1.4 Study Outcome Measures

Primary Outcome Measures

A1: Success rates of conduction system lead implant (novel workflow vs conventional methods)

B1: Assess accuracy of conduction system diagnosis by the device with additional information from 2-lead ECG

- A2: Procedure and fluoroscopy times of the streamlined workflow to current conventional methods *of His-bundle and Left-bundle pacing*
- A2: Procedure and fluoroscopy times of the streamlined workflow of conduction system implant to current *right ventricular pacing*
- A2: Assess capture threshold of His-bundle and Left-bundle pacing from the optimised workflow to that of conventional methods of conduction system implantation
- A2: Define left bundle area capture diagnostics and delineate differences between left ventricular septal pacing.
- B2: Improvement in device battery life with novel device algorithm applied

5 Participant Entry

- 5.1 Pre-registration Evaluations
- 5.2 Inclusion Criteria
 - 1. Patients with a ventricular pacing indication: high grade atrioventricular block and symptomatic trifasicular, bifasicular block or left bundle branch block LBBB for cardiac resynchronisation therapy
 - 2. Adults willing to take part (ages 18 100 years old)
 - 3. Able to give consent.

5.3 Exclusion Criteria

- 1. Unable to give consent
- 2. Children age < 18 years and adults > 100 years old
- 3. Pregnant patients As per standard of care, female patients of child-bearing age will have a urine pregnancy test prior to their procedure.

5.4 Withdrawal criteria

The research protocol will be terminated early if

- 1. Patients lose their capacity to consent or become clinically unstable
- 2. The patient chooses to withdraw from the study
- 3. The sponsor, the chief investigator or the research team review the data and decide to stop the study

5.5 Consent

Patients will be identified by members of their direct care team when they attend clinic appointments or are admitted as an inpatient to the hospital. Patient records may be reviewed to assess suitability and this will be performed by members of the direct care team. Participation in the study will be discussed with the patients by their direct care team and information will only be passed on to the research team with the patients consent. Verbal consent will be gained by the direct care team for personal contact information to be shared with the research team. This will be documented in the patient notes.

The direct care team will make patients aware that participation is voluntary and that if they do not wish to participate it will not affect their usual care.

Consent for the study of the prospectively recruited patients will be obtained by a member of the research team, this will be a physician who is experienced in performing conduction system implantation. Patients will have details of the study discussed with them and any family members or friends the patients wish to be present. They will also be provided with written information (patient information sheets). Patients will be given as much time as they wish, with a minimum of at least 24 hours, to decide whether they wish to participate in the study and will be offered additional visits to further discuss the study if they wish. Patients are able to withdraw their consent from the study at any time. Patients will be made aware that their participation is voluntary and that if they do not want to take part it will not affect their usual care. Patients who agree to take part in the study will sign a consent form, a copy of the form will be given to the patients and a second copy will be kept in their study record file. A copy will also be kept in the site file.

6 Adverse events

6.1 Definitions

Adverse Event (AE): any untoward medical occurrence in a patient or clinical study subject.

Serious Adverse Event (SAE): any untoward and unexpected medical occurrence or effect that:

- Results in death
- Is life-threatening refers to an event in which the subject was at risk of death at the time of the event; it does not refer to an event which hypothetically might have caused death if it were more severe
- Requires hospitalisation, or prolongation of existing inpatients' hospitalisation
- Results in persistent or significant disability or incapacity
- Is a congenital anomaly or birth defect

Medical judgement should be exercised in deciding whether an AE is serious in other situations. Important AEs that are not immediately life-threatening or do not result in death or hospitalisation but may jeopardise the subject or may require intervention to prevent one of the other outcomes listed in the definition above, should also be considered serious.

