1.3 Burden/Risk

The main burdens for the patient include:

- The extra time taken to perform the experiments and experimental procedures during their scheduled clinical procedure due to the additional diagnostic investigations. The right heart electro-anatomical mapping will add 10 minutes. The echocardiography will add an additional 5 minutes. Those who consent to left ventricular maps will have an additional 14 minutes (7 minutes per map).
- 2. The extra access in the groin in those who consent to have an intracardiac echocardiography or left ventricular map (femoral vein and artery respectively).
- 3. The extra procedure of transoesophageal echocardiography in those who consent for this
- 4. Patients receiving unconventional therapy with conduction system lead implantation

The burden will be mitigated by the minimum extra time being used to complete the experiments, the use of local anaesthetic and the immediate removal of extra research related sheaths as soon as they are not needed

The main risks for the patient are:

A conduction system pacing wire is not known to have a higher complication rate compared to a conventional pacing wire. Conduction system pacing wires have been shown to be as effective as conventional pacing wires at preventing slow heart rates and improving heart pumping. If a complication occurs and the conduction system pacing wire cannot be implanted or does not perform as expected during follow-up a procedure will be performed to convert your pacing system to a conventional pacing system.

The additional risks of arterial tube placement include:

- 1% risk of bruising around the area
- 1 in 1000 risk of damage to the blood vessels requiring surgery
- Less than 1 in 500 risk of stroke
- The additional risks of transoesophageal echocardiogram include

• 1% risk of damaging the food-pipe or wind-pipe including a 1 in 1000 risk of perforating the food-pipe.

The additional risks of intracardiac echocardiogram include

- 1% risk of bruising around the access area in the leg
- Less than 1 in 1000 risk of heart perforation

The additional risks of electro-anatomical mapping include

Less than 1 in 1000 risk of heart perforation

Therefore, the overall risk of serious complications arising from taking part in the research study are less than 4 in 1000 (0.4%)

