6.2 Reporting Procedures

All adverse events should be reported. Depending on the nature of the event the reporting procedures below should be followed. Any questions concerning adverse event reporting should be directed to the Chief Investigator in the first instance.

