6.3 Non serious AEs

All such events, whether expected or not, should be recorded.

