6.4 Serious AEs

An SAE form should be completed and faxed to the Chief Investigator within 24 hours. However, hospitalisations for elective treatment of a pre-existing condition do not need reporting as SAEs.

All SAEs should be reported to the West of Scotland (REC 4) where in the opinion of the Chief Investigator, the event was:

- 'related', ie resulted from the administration of any of the research procedures; and
- 'unexpected', ie an event that is not listed in the protocol as an expected occurrence

Reports of related and unexpected SAEs should be submitted within 15 days of the Chief Investigator becoming aware of the event, using the NRES SAE form for non-IMP studies. The Chief Investigator must also notify the Sponsor of all related and unexpected SAEs.

Local investigators should report any SAEs as required by their Local Research Ethics Committee, Sponsor and/or Research & Development Office.

Contact details for reporting SAEs [contact] [name] email: [contact] Please send SAE forms to: Hammersmith Hospital, [name]. [contact] (Mon to Fri 09.00 – 17.00)

7 Assessment and Follow-up

Patients will be followed up for a 1 year period. During this time they will undergo the device interrogation and wound check at 6 weeks as part of standard clinical care. One year after device implantation, patients will undergo a device interrogation follow-up appointment. Any incidental findings that we identify during the study will be reviewed by the research team and reported to the GP and also the cardiology team normally looking after the patient.

Definition of end of Study

The end of the study will be defined as completion of the 1 year follow-up of the 100 prospectively recruited patients for the invasive aspect of the study. This will be the date of the final visit of the last participant at 1 year.

8 Statistics and data analysis

The following statistical analysis has been reviewed and approved by our statistician, [name].

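### The SAE definition in section 6.1 includes expectedness, which section 6.4 then uses to select among SAEs; the two need reconciling so that seriousness alone triggers the 24-hour form

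*Protocol*

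**What the plan says.** Section 6.1 of the protocol defines an adverse event with no condition on expectedness. It then defines an SAE as "any untoward and unexpected medical occurrence or effect that" meets one of the listed criteria: death, threat to life, hospital admission, disability or congenital anomaly. A medical-judgement clause follows for other situations. Its second sentence concerns "Important AEs that are not immediately life-threatening or do not result in death or hospitalisation but may jeopardise the subject", or that may need intervention.

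Section 6.2 states the general rule, "All adverse events should be reported". It sends the reader to the procedures below according to the nature of the event, and refers questions to the Chief Investigator.

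Section 6.3 deals with non-serious events: "All such events, whether expected or not, should be recorded".

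Section 6.4 deals with SAEs: "An SAE form should be completed and faxed to the Chief Investigator within 24 hours". Elective admissions for a pre-existing condition are exempt. SAEs go to the ethics committee if the Chief Investigator judges them both related and unexpected, where unexpected means "an event that is not listed in the protocol as an expected occurrence". The time limit is stated as "Reports of related and unexpected SAEs should be submitted within 15 days of the Chief Investigator becoming aware of the event", and the sponsor must be told of the same subset. Local investigators are also to report SAEs as their local ethics committee, the sponsor or the R&D office requires.

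The Burden/Risk section (numbered 1.3, within Methodology) names serious complications of the added research procedures and gives rates for them. It does not call them expected occurrences, and no other list in the protocol carries that label.

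**The concern.** Seriousness and expectedness are separate attributes of an event. Section 6.4 treats them separately: it takes the SAEs and filters them by relatedness and expectedness. Section 6.1 merges them, so that an expected SAE cannot exist and the second half of the 6.4 filter has nothing to remove. Section 6.3 sharpens the contrast, because it covers non-serious events regardless of expectedness and no matching words cover serious ones.

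What is at stake is consistent and timely safety oversight. The SAE form is the only route to the Chief Investigator with a stated deadline. Section 6.4 leaves expectedness to the Chief Investigator's opinion. Taken at its word, 6.1 moves that judgement to whoever decides whether to complete the form, before the Chief Investigator has seen the event by that route.

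**Working it through.** The protocol gives no figure to reproduce here. The check is a comparison of the sections under each possible meaning of expected, followed by a rough event count.

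**Reading 1: nothing is listed as expected.** This is the literal position, since no list carries that label.
- Every event that meets a seriousness criterion is unexpected, so it is an SAE under 6.1.
- The 24-hour form applies to all of them.
- Every related SAE goes to the ethics committee and the sponsor.
- The word *unexpected* does no work in 6.1 or 6.4. The text is redundant, but there is no gap.

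**Reading 2: the Burden/Risk complications are treated as expected.** This is an inference by the reader. Take a stroke after arterial access.
- Section 6.1: it is not unexpected, so it falls outside the SAE definition.
- Section 6.4: the form and the 24-hour limit attach to SAEs, so they do not literally apply.
- Section 6.3: the event is not non-serious, so this does not apply either.
- What remains is the general statement in 6.2, the referral of questions to the Chief Investigator, and the discretionary medical-judgement clause.
- Onward reporting: the event is not unexpected, so it does not meet the 6.4 criteria for the ethics committee or the sponsor, even if related. Under Reading 1 a related stroke would meet them. The choice of reading therefore changes onward notification as well as the form.
- The sentence on local investigators is not limited to related and unexpected events, but it too presupposes that the event is an SAE.

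**How many events.** The inputs are the Burden/Risk rates taken as upper values, applied to the research procedures in the derivation cohort. Numbers of patients come from section 4.1.

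| Procedure | Patients | Rate | Expected events |
|---|---|---|---|
| Arterial access (vessel surgery, stroke) | 15 | 1/1000 + 1/500 | 15 × 0.003 = 0.045 |
| Right ventricular mapping (heart perforation) | 50 | 1/1000 | 0.050 |
| ICE or TOE (heart or food-pipe perforation) | 0 to 50 | 1/1000 | 0 to 0.050 |
| Left ventricular mapping, if it carries its own perforation risk | 15 | 0 or 1/1000 | 0 or 0.015 |

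The number having ICE or TOE is not given, and transthoracic echocardiography may replace them, hence the range of 0 to 50. The perforation rate is quoted for electro-anatomical mapping as a whole, so it is unclear whether the left-sided map adds to it.

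- Lowest total: 0.045 + 0.050 = 0.095.
- Highest total: 0.095 + 0.050 + 0.015 = 0.160.
- Chance of at least one event, lowest: 1 − (0.999 × 0.998)^15 × 0.999^50 = 0.091.
- Chance of at least one event, highest: 1 − (0.999 × 0.998)^15 × 0.999^50 × 0.999^50 × 0.999^15 = 0.148.

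Bruising, and food-pipe or wind-pipe damage short of perforation, are not counted as serious. The protocol's own overall figure for serious complications, under 0.4%, is too small to include those 1% risks.

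That overall figure gives a separate upper limit: 50 × 0.004 = 0.2 events, with a chance of at least one of 1 − 0.996^50 = 0.182. It is a different bound and does not verify the sum above.

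**The case against.** The strongest reply is that the gap depends on something the protocol does not say. The Burden/Risk section never labels its complications as expected, so on the literal text every serious event gets the 24-hour form. Other wording also favours the safe reading. Section 6.2 routes events by their nature, and the two headings below it divide them by seriousness alone. The exemption for elective admissions in 6.4 would be largely unnecessary if 6.1 had already removed expected events. Anyone in doubt is told to ask the Chief Investigator. The medical-judgement clause speaks of an AE, which has no expectedness condition, and its alternatives are joined by *or*. It could therefore bring in a hospitalised stroke that is not immediately life-threatening, or vessel damage that needs intervention.

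Most of this stands. It makes the gap conditional and narrows it. It does not remove the conflict between 6.1 and 6.4, which remains on the literal reading as a redundant word in both places. The judgement clause is discretionary and does not clearly reach an expected event that is immediately life-threatening and fatal. The Burden/Risk section is also the natural place for staff to look when 6.4 refers them to occurrences listed in the protocol.

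A reader might go further and infer that the protocol leaves serious procedural complications unreported. The documents do not support that: 6.2 requires all adverse events to be reported on any reading.

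**Conclusion.** Sections 6.1 and 6.4 conflict, and the definition in 6.1 is wrong as written. The practical consequence is conditional. If the Burden/Risk complications are taken as expected, such an event lacks a clearly stated form and deadline and drops out of ethics-committee and sponsor notification. If they are not, the wording is only redundant.

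The size is small: about 0.1 to 0.16 expected events in the derivation cohort. This takes the protocol's rates as upper values and depends on how many patients have ICE or TOE and on whether left ventricular mapping carries its own perforation risk. It covers only the added research procedures in those 50 patients, so it is not a ceiling on all serious events in the study. No efficacy outcome or analysis is affected.

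**What to change.** Delete the requirement of unexpectedness from the SAE definition in 6.1 (two words), so that seriousness alone triggers the SAE form and the 24-hour deadline. Keep relatedness and unexpectedness only in 6.4, as the criteria for onward reporting.

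The deletion alone leaves 6.4 pointing to a list that the protocol does not identify. The same amendment should therefore state in 6.4 whether the Burden/Risk complications are the expected occurrences it refers to.

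The cost is one short protocol amendment and, for the derivation-cohort research procedures, about 0.1 to 0.16 additional SAE forms on average, and only if staff would otherwise have withheld them.

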6.2 Reporting Procedures

All adverse events should be reported. Depending on the nature of the event the reporting procedures below should be followed. Any questions concerning adverse event reporting should be directed to the Chief Investigator in the first instance.

6.3 Non serious AEs

All such events, whether expected or not, should be recorded.

6.4 Serious AEs

An SAE form should be completed and faxed to the Chief Investigator within 24 hours. However, hospitalisations for elective treatment of a pre-existing condition do not need reporting as SAEs.

All SAEs should be reported to the West of Scotland (REC 4) where in the opinion of the Chief Investigator, the event was:

- 'related', ie resulted from the administration of any of the research procedures; and
- 'unexpected', ie an event that is not listed in the protocol as an expected occurrence

Reports of related and unexpected SAEs should be submitted within 15 days of the Chief Investigator becoming aware of the event, using the NRES SAE form for non-IMP studies. The Chief Investigator must also notify the Sponsor of all related and unexpected SAEs.

Local investigators should report any SAEs as required by their Local Research Ethics Committee, Sponsor and/or Research & Development Office.

Contact details for reporting SAEs [contact] [name] email: [contact] Please send SAE forms to: Hammersmith Hospital, [name]. [contact] (Mon to Fri 09.00 – 17.00)

7 Assessment and Follow-up

Patients will be followed up for a 1 year period. During this time they will undergo the device interrogation and wound check at 6 weeks as part of standard clinical care. One year after device implantation, patients will undergo a device interrogation follow-up appointment. Any incidental findings that we identify during the study will be reviewed by the research team and reported to the GP and also the cardiology team normally looking after the patient.

Definition of end of Study

The end of the study will be defined as completion of the 1 year follow-up of the 100 prospectively recruited patients for the invasive aspect of the study. This will be the date of the final visit of the last participant at 1 year.

8 Statistics and data analysis

The following statistical analysis has been reviewed and approved by our statistician, [name].

In **Study A**, I want the validation cohort to be big enough to calculate the success rate percentage with an error margin (standard error) of <10 percentage points in line with primary outcome A1. Similarly, for **Study B**, I want the validation cohort to show the accuracy of my algorithm with an SE under 10 percentage points in line with primary outcome B1. The standard error of a proportion p, in a sample of n patients, is $\sqrt{[p(1-p)/n]}$, i.e. $n=p(1-p)/SE^2$. Applying SE=0.1 (worst-case proportion 0.5) reveals the bare-minimum n required is $0.5*0.5/0.1^2=25$. I will have 50, to ensure the SE <10 percentage points.

Figure 1: A illustration to demonstrate the primary and secondary outcomes of Study A and Study B. * Sample size calculations indicate 50 patients will provide >80% power (see Section 8, statistics and data analysis for more information)

9 Regulatory issues

9.1 Ethics approval

The Study Coordination Centre has obtained approval from the "Name of REC when allocated" and Health Research Authority (HRA). The study must also receive confirmation of capacity and capability from each participating NHS Trust before accepting participants into the study or any research activity is carried out. The study will be conducted in accordance with the recommendations for physicians involved in research on human subjects adopted by the 18th World Medical Assembly, Helsinki 1964 and later revisions.

9.2 Consent

Consent to enter the study must be sought from each participant only after a full explanation has been given, an information leaflet offered and time allowed for consideration. Signed participant consent should be obtained. The right of the participant to refuse to participate without giving reasons must be respected. After the participant has entered the study the clinician remains free to give alternative treatment to that specified in the protocol at any stage if he/she feels it is in the participant's best interest, but the reasons for doing so should be recorded. In these cases the participants remain within the study for the purposes of follow-up and data analysis. All participants are free to withdraw at any time from the protocol treatment without giving reasons and without prejudicing further treatment.

9.3 Confidentiality

The Chief Investigator will preserve the confidentiality of participants taking part in the study and is registered under the Data Protection Act. Data will be pseudonymised.

9.4 Indemnity

Imperial College London hold negligent harm and non-negligent harm insurance policies which apply to this study.

9.5 Sponsor

Imperial College London will act as the main Sponsor for this study. Delegated responsibilities will be assigned to the NHS trusts taking part in this study.

9.6 Funding

The British Heart Foundation.

9.7 Audits

The study may be subject to inspection and audit by Imperial College London under their remit as sponsor and other regulatory bodies to ensure adherence to GCP and the UK Policy Frame Work for Health and Social Care Research

10 Study Management

The day-to-day management of the study will be co-ordinated by [name].

11 Publication Policy

Our aim to publish in a major international cardiology journal and present at international cardiology conferences.

12 Appendix

Intrinsic	Degree of BBB	His Bundle Pacing		
QRS	correction	S-HPB	NS HBP	
Normal QRS	Nil	Stim-QRS _{end} = H-QRS _{end} Paced QRSd = intrinsic QRSd Stim-vent = H-vent Single capture threshold	Stim-QRS _{end} < H-QRS _{end} +/- pseudodelta wave Paced QRSd > intrinsic QRSd Two distinct capture thresholds	
LBBB	Full correction	Normal QRS appearance Stim-QRS _{end} < H-QRS _{end} Paced QRSd <120ms < intrinsic QRSd	Pre-excited normal QRS appearance Stim-QRS _{end} usually < H-QRS _{end} Paced QRSd > 120ms Paced QRSd usually < intrinsic QRSd	
	Partial correction	LBBB morphology Stim-QRS _{end} < H-QRS _{end} Paced QRSd < instrinsic QRSd	LBBB QRS morphology Stim-QRS _{end} < / = H-QRS _{end} Paced QRSd >120ms Paced QRSd usually < intrinsic QRSd	
	No correction	Stim-QRS _{end} = H-QRS _{end} LBBB morphology Paced QRSd = intrinsic QRSd	LBBB morphology Paced QRSd > intrinsic QRSd	
	Myocardium only capture	LBBB morphology Stim QRSend usually > H-QRS _{end} Paced QRSd > intrinsic QRSd		
RBBB	Bundle recruitment	Normal QRS appearance Stim-QRS _{end} < H-QRS _{end} Paced QRSd < 120ms < intrinsic QRSd	Pre-excited normal QRS appearance Stim-QRS _{end} < H-QRS _{end} Paced QRSd =/ intrinsic QRSd	
	Resynchronisation	NS-HBP without right bundle recruitment Pre excited normal QRS appearance Stim-QRS _{end} < H-QRS _{end} /paced QRSd < intrinsic QRSd		
	No bundle recruitment or resynchronisation	S-HBP without right bundle recruitment RBBB morphology Stim-QRS _{end} = H-QRS _{end} /paced QRSd = intrinsic QRSd		
	Myocardium only capture	LBBB morphology Stim-QRS _{end} > H-QRS _{end} /paced QRSd >intrinsic QRSd		

Table 1: Time consuming and complex criteria for conduction system capture. (1,11,12)

13 References

